## 6.2. Background Characteristics

### 6.2.1. Subject Disposition

The number and percentage of subjects in the following categories will be summarized by treatment group as defined in Section 4 based on the Randomization Set:

- Randomization Set
- FAS
- PP
- Safety Set
- Solicited Safety Set

Percentages will be based on the number of subjects in the treatment group within the Randomization Set. For Solicited Safety Set, the percentage will be based on the number of subjects in the treatment group within the Safety Set (as treated).

Summary of reasons for subjects excluded from PP will also be provided.

The number of subjects in the following categories will be summarized based on subjects screened:

- Number of subjects screened
- Number and percentage of screen failure subjects and the reason for screen failure

The percentage of subjects who screen failed will be based on the number of subjects screened. The reason for screen failure will be based on the number of subjects who screen failed.

The number and percentage of subjects in each of the following disposition categories will be summarized by treatment group based on the Randomization Set:

- Received IP
- Completed study
- Prematurely discontinued the study and the reason for discontinuation

This study treatment only consists of a 1-dose, thus discontinuation from study treatment is not applicable to this study. A subject is considered to have completed the study if he or she has completed the study including the last scheduled procedure as shown in the SoE (Table 1 in the Protocol).

A subject disposition listing will be provided, including informed consent, subjects who received IP, subjects who completed study, subjects who discontinued from study, with reasons for discontinuation. A separate listing will be provided for screen failure subjects with reasons for screen failure.

### **6.2.2. Demographics and Baseline Characteristics**

Descriptive statistics will be calculated for the following continuous demographic and baseline characteristics: age (years), weight (kg), height (cm), and body mass index (BMI) ( $\text{kg}/\text{m}^2$ ). Number and percentage of subjects will be provided for categorical variables such as age group (18 to 49 years old and 50 to 75 years old), gender, race, ethnicity. The summaries will be presented by treatment group as defined in Section 4 based on the FAS.

In addition, randomized subjects with any inclusion and exclusion criteria deviation will also be provided in a listing.

### **6.2.3. Medical History**

Medical history data will be coded by system organ class (SOC) and preferred term (PT) using the Medical Dictionary for Regulatory Activities (MedDRA).

The number and percentage of participants with any medical history will be summarized by SOC and PT based on the Safety Set. A participant will be counted only once for multiple events within each SOC and PT. SOC will be displayed in internationally agreed order. PT will be displayed in descending order of frequency of mRNA-1073 CCI group and then alphabetically within SOC.

Medical history data will be presented in a listing.

### **6.2.4. Prior and Concomitant Medications**

Prior and concomitant medications and non-study vaccination will be coded using the World Health Organization (WHO) drug dictionary (WHODD). The summary of concomitant medications will be based on the Safety Set. Categorization of prior, concomitant, and post medications is summarized in [Appendix C Table 5](#).

The number and percentage of subjects using concomitant medications and non-study vaccination during the 7-day follow-up period (i.e., on the day of injection and the 6 subsequent days) and during the 28-day follow-up period after the injection (i.e., on the day of injection and the 27 subsequent days) will be summarized by vaccination group (as defined in [Section 6.1](#)) as follows:

- Any concomitant medications and non-study vaccination within 7 days post-injection
- Any concomitant medications and non-study vaccination within 28 days post-injection
- Seasonal influenza or COVID-19 vaccine within 28 days post-injection
- Antipyretic or analgesic medication within 28 days post-injection

A summary table of concomitant medications and non-study vaccination that continued or newly received at or after the injection through 28 days will be provided by PT in descending frequency based on mRNA-1073 **CCI** group.

Medications taken to prevent or treat pain or fever will be collected in the electronic diary (eDiary), and summaries will be provided based on the Solicited Safety Set by vaccination group (and then by age group) as defined in [Section 6.1](#), including within 7 days after injection, beyond 7 days after injection, and any time after injection.

Prior, concomitant and post medications and non-study vaccination will be presented in a listing. Medications taken to prevent or treat pain or fever will also be presented in a listing.

Concomitant Procedures will be presented in a listing.

#### **6.2.5. Study Exposure**

Study vaccine administration data will be presented in a listing. Subjects with any dosing errors will also be presented in a separate listing.

Study duration will be summarized since randomization, and since the study injection based on Safety Set.

#### **6.2.6. Major Protocol Deviations**

Major protocol deviations are a subset of protocol deviations that may significantly impact the completeness, accuracy, or reliability of the study data or that may significantly affect a subject's rights, safety, or well-being. Major protocol deviations rules will be developed and finalized before database lock.

The number and percentage of the subjects with each major protocol deviation type will be provided by treatment group, as defined in [Section 6.1](#), based on the Randomization Set.

Major protocol deviations will be presented in a listing.

#### **6.2.7. COVID-19 Impact**

A listing will be provided for COVID-19 impact on missed or out of window visits or assessments for subjects in Safety Set.

### 6.3. Efficacy analysis

While the study is not powered for efficacy assessments, symptoms of infection with respiratory pathogens will be tracked as an exploratory objective in this study. All participants will provide nasopharyngeal (NP) swab samples before the injection on Day 1 for assessment of infection with respiratory pathogens, including influenza viruses and SARS-CoV-2. Additionally, participants will be instructed to report via Symptom Reporting eDiary or telephone calls whether ILI/COVID-19 symptoms have been experienced (see [Section 8.4.5](#) and [Section 8.4.6 in Protocol](#) for symptoms), 2 times weekly from Day 1 through Day 29 and once weekly from Day 30 through Day 181/EoS.

#### 6.3.1. Influenza infection

Influenza infection during the study is an efficacy endpoint, and the analyses of influenza infection by RT-PCR test may be performed using the FAS.

1. A protocol-defined ILI is determined by the occurrence of at least 1 respiratory illness symptom concurrently with at least 1 systemic symptom, or the occurrence of any 2 or more respiratory symptoms defined below:
  - Sore throat
  - Cough/rhinorrhea/nasal congestion ( $\geq 1$  of the 3 symptoms count as 1 respiratory symptom)
  - Sputum production
  - Wheezing
  - Difficulty breathing
2. A CDC defined ILI is defined as body temperature  $\geq 37.8^{\circ}\text{C}$  ( $100^{\circ}\text{F}$ ) accompanied by cough and/or sore throat.
3. An RT-PCR confirmed ILI is defined as a positive influenza result by RT-PCR done at any setting during the study period.

The following summaries will be provided for influenza infection:

- RT-PCR test results at baseline will be summarized by vaccination group. Participants with positive influenza results at baseline will be presented in a listing.
- The number and percentage of participants with at least one positive influenza result at post-baseline will be provided by vaccination group. Participants with at least one positive influenza result at post-baseline will be presented in a listing.
- Participants with RT-PCR confirmed ILI will be presented in a listing.

### 6.3.2. SARS-CoV-2 Infection

- Symptomatic COVID-19 is defined by the presence of one of the below CDC-listed symptoms (CDC [2021c](#)) and a positive RT-PCR test on a respiratory sample. Fever (temperature  $\geq 38.0^{\circ}\text{C}$  [ $100.4^{\circ}\text{F}$ ]) or chills (of any duration)
- Cough (of any duration)
- Shortness of breath and/or difficulty breathing (of any duration)
- Nausea, vomiting or diarrhea (of any duration)
- Fatigue (lasting  $\geq 48$  hours)
- Muscle or body aches (lasting  $\geq 48$  hours)
- Headache (lasting  $\geq 48$  hours)
- New loss of taste and/or smell (lasting  $\geq 48$  hours)
- Sore throat, congestion, or runny nose (lasting  $\geq 48$  hours)

Asymptomatic SARS-CoV-2- infection is defined as a positive RT-PCR test on a respiratory sample in the absence of symptoms or a positive serologic test for anti-nucleocapsid antibody after a negative test result at the time of enrollment, with the serologic assay detecting previously resolved SARS-CoV-2 infections that may have occurred between visits, and the RT-PCR to detect active viral infection at the time of a visit. The following summaries will be provided for SARS-CoV-2- infection:

- RT-PCR test results at baseline will be summarized by test and vaccination group. Participants with positive SARS-CoV-2- results at baseline will be presented in a listing.

- The number and percentage of participants with at least one positive SARS-CoV-2- result at post-baseline will be provided by vaccination group. Participants with at least one positive SARS-CoV-2- result at post-baseline will be presented in a listing.
- Participants with RT-PCR confirmed SARS-CoV-2 infection will be presented in a listing.

## 6.4. Safety Analysis

Safety and reactogenicity will be assessed by clinical review of all relevant parameters including solicited ARs (local and systemic), unsolicited AEs, SAEs, MAAEs, AESI, AEs leading to withdrawal from study vaccine and/or study participation, vital signs, and physical examination findings. Solicited ARs and unsolicited AEs will be coded by SOC and PT according to the MedDRA.

All safety analyses will be based on the Safety Set, except summaries of solicited ARs, which will be based on the Solicited Safety Set. All safety analyses will be provided by vaccination group.

### 6.4.1. Solicited Adverse Reactions

An AR is any AE for which there is a reasonable possibility that the test product caused the AE. The term “Solicited Adverse Reactions” refers to selected signs and symptoms occurring after injection administration during a specified post-injection follow-up period (day of injection and 6 subsequent days). An eDiary will solicit daily the participant on the occurrence and intensity of selected signs and symptoms using a pre-defined structured checklist.

The following local ARs will be solicited by the eDiary: injection site pain, injection site erythema (redness), injection site swelling/induration (hardness), and underarm gland swelling or tenderness.

The following systemic ARs will be solicited by the eDiary: headache, fatigue, myalgia (muscle aches all over the body), arthralgia (aches in several joints), nausea/vomiting, chills, and fever.

The solicited ARs will be graded based on the grading scales presented in Table 6 in the protocol, modified from the Toxicity Grading Scale for Healthy Adult and Adolescent Volunteers Enrolled in Preventative Vaccine Clinical Trials ([DHHS 2007](#)).

If a solicited local or systemic AR continues beyond 7 days post-injection, the subject will be prompted to capture solicited local or systemic AR in the eDiary until resolution, not to exceed 28 days after study injection.

All solicited ARs (local and systemic) will be considered causally related to dosing.

Analyses of solicited ARs will be provided by vaccination group based on the Solicited Safety Set. Summaries of local solicited ARs will be also presented by vaccination group and injection content received in the corresponding side/deltoid.

The number and percentage of participants with any solicited local ARs, solicited systemic ARs, and solicited ARs during the 7-day follow-up period after the injection will be summarized, along with the number of events under each category. A two-sided 95% exact CI using the Clopper-Pearson method will be provided for the percentage of participants who reported any solicited local AR, solicited systemic AR, or any solicited AR.

The number and percentage of participants who reported each individual solicited local AR and solicited systemic AR during the 7-day follow-up period after injection will be provided by severity grade.

The number and percentage of subjects experiencing fever (a temperature greater than or equal to 38°C/100.0°F by the oral route) by severity grade and the number and percentage of subjects experiencing a fever of Grade 3 or higher temperature (a temperature greater than or equal to 39.0°C/102.1°F by the oral route) will be provided.

The onset of individual solicited AR is defined as the time point after injection at which the respective solicited AR first occurred. The number and percentage of subjects with onset of individual solicited AR will be summarized by study day relative to the injection (Day 1 through Day 7). The day of onset of each solicited AR within 7 Days will be summarized.

The duration of local or systemic solicited ARs, along with the specific individual solicited ARs, will be calculated as: reaction end date – reaction start date +1, no matter it is intermittent or continued or if the solicited AR continues beyond 7 days. The duration of each solicited AR within 7 Days will be summarized.

All solicited ARs that continue beyond 7 days post-injection will be summarized.

All delayed ARs with onset day after 7 days post injection will also be summarized.

These summaries may be provided for additional subgroups of selected baseline characteristics.

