## 3. Study Endpoints

### 3.1. Primary Endpoints

The primary objective will be evaluated by the following endpoints:

- Frequency and grade of each solicited local and systemic reactogenicity AR during a 7-day follow-up period post vaccination
- Frequency and severity of any unsolicited adverse events (AEs) during the 28-day follow-up period post vaccination
- Frequency of any serious adverse events (SAEs), adverse events of special interest (AESIs), medically attended adverse events (MAAEs), and AEs leading to discontinuation from Day 1 to Day 181/EoS

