**Table 1 Study Arms**

#	Group Name	Sample Size (N=550)
1	mRNA-1273 CCI + placebo	50
2	mRNA-1010 CCI + placebo	100
3	mRNA-1010 CCI + mRNA-1273 CCI co-administration	100
4	mRNA-1073 CCI + placebo	100
5	mRNA-1073 CCI + placebo	100
6	mRNA-1073 CCI + placebo	100

All participants of the study will participate in a Screening period (up to 28 days before Day 1), treatment period (single dose of vaccine on Day 1), and a follow-up period (up to 6 months after vaccination). The study schema is presented in [Figure 1](#). Please refer to Table 1 in the protocol for Schedule of Events (SoE).

**Figure 1** Study Schema

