#### 9.1.6. Appendix F Severity Grading of Vital Sign Abnormalities

Vital Signs*	Mild (Grade 1)	Moderate (Grade 2)	Severe (Grade 3)	Potentially Life Threatening (Grade 4)
Fever (°C)** (°F)**	38.0 – 38.4 100.4 – 101.1	38.5 – 38.9 101.2 – 102.0	39.0 – 40 102.1 – 104	> 40 > 104

Tachycardia - beats per minute	101 – 115	116 – 130	> 130	ER visit or hospitalization for arrhythmia
Bradycardia - beats per minute***	50 – 54	45 – 49	< 45	ER visit or hospitalization for arrhythmia
Hypertension (systolic) - mm Hg	141 – 150	151 – 155	> 155	ER visit or hospitalization for malignant hypertension
Hypertension (diastolic) - mm Hg	91 – 95	96 – 100	> 100	ER visit or hospitalization for malignant hypertension
Hypotension (systolic) – mm Hg	85 – 89	80 – 84	< 80	ER visit or hospitalization for hypotensive shock
Respiratory Rate – breaths per minute	17 – 20	21 – 25	> 25	Intubation

\* Participant should be at rest for all vital sign measurements.

\*\* Oral temperature; no recent hot or cold beverages or smoking.

\*\*\* When resting heart rate is between 60 – 100 beats per minute. Use clinical judgement when characterizing bradycardia among some healthy participant populations, for example, conditioned athletes.

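### SAP Section 6.4.1 gives the solicited-fever cut-off as 38°C/100.0°F, but 38°C is 100.4°F, so readings of 100.0–100.3°F are fever in one unit and not in the other

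*SAP*

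**What the plan says.** Section 3.1 makes this a primary endpoint: "Frequency and grade of each solicited local and systemic reactogenicity AR during a 7-day follow-up period post vaccination". Fever is one of the seven systemic reactions listed in Section 6.4.1. The data come from participants' diaries: "An eDiary will solicit daily the participant on the occurrence and intensity of selected signs and symptoms". On grading, the same section states: "The solicited ARs will be graded based on the grading scales presented in Table 6 in the protocol". It then asks for the number and percentage of subjects "experiencing fever (a temperature greater than or equal to 38°C/100.0°F by the oral route) by severity grade", and for a separate count of Grade 3 or higher fever at 39.0°C/102.1°F.

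Three other places in the SAP state a temperature threshold in both units:

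- Section 6.3.2: "Symptomatic COVID-19 is defined by the presence of one of the below CDC-listed symptoms", together with a positive RT-PCR test. The first listed symptom includes fever at 38.0°C, with 100.4°F in brackets.
- Section 6.3.1: "A CDC defined ILI is defined as body temperature" of at least 37.8°C, with 100°F in brackets, plus cough and/or sore throat.
- Appendix F, Grade 1 fever, oral, in °C and then °F: "38.0 – 38.4 100.4 – 101.1".

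**The concern.** Section 6.4.1 combines the Celsius value of one threshold used in the SAP with the Fahrenheit value of another. A programmer could follow either, and the SAP does not say which governs or in which unit the diary temperature is analysed.

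Under the Fahrenheit value, a participant whose highest reading is 100.0–100.3°F has fever. Under the Celsius value the same participant does not. Four outputs could differ:

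- **Fever count.** The count and percentage could rise.
- **Totals by grade.** If the grading scale starts at 100.4°F, as Appendix F does, the fever total could exceed the sum of its grades.
- **Any-systemic and any-solicited percentages.** These carry Clopper-Pearson intervals and could rise too.
- **Onset and duration.** A participant at 100.2°F on Day 1 and 101.0°F on Day 2 has fever onset on Day 1 by the Fahrenheit value and on Day 2 by the Celsius value. The start date used for duration moves with it.

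**Working it through.** **Inputs.** Section 6.4.1: 38°C/100.0°F for fever and 39.0°C/102.1°F for Grade 3 or higher. Section 6.3.2: 38.0°C/100.4°F. Section 6.3.1: 37.8°C/100°F. Appendix F, Grade 1: 38.0–38.4°C/100.4–101.1°F. Table 1: one group of 50 and five of 100. Section 4.4: the two age strata are balanced within each group.

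**Formulas.** F = C × 9/5 + 32 and C = (F − 32) × 5/9.

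**1. Can the stated pair be reproduced?** No.
- 38.0 × 9/5 + 32 = 100.4°F, not 100.0°F.
- (100.0 − 32) × 5/9 = 37.78°C, which is 37.8°C to one decimal and not 38.0°C.
- Rounding to a whole degree would turn 37.78 into 38. However, the same sentence works to 0.1° for the Grade 3 cut-off, and so does Appendix F.

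**2. Do the other pairs reproduce?**

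| Place | Stated pair | °C converted to °F | Difference |
|---|---|---|---|
| 6.4.1, fever | 38 / 100.0 | 100.4 | 0.4°F |
| 6.3.2, fever item | 38.0 / 100.4 | 100.4 | none |
| Appendix F, Grade 1 lower bound | 38.0 / 100.4 | 100.4 | none |
| 6.3.1, CDC-defined ILI | 37.8 / 100 | 100.04 | 0.04°F (rounding) |
| 6.4.1, Grade 3 or higher | 39.0 / 102.1 | 102.2 | 0.1°F |

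The Grade 3 pair is 0.1°F (0.06°C) off but matches Appendix F. The fever cut-off is the only pair with a material gap.

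**3. Which readings fall in the gap?** 100.4 − 100.0 = 0.4°F, and 0.4 × 5/9 = 0.22°C. At 0.1°F resolution there are four readings:
- 100.0°F = 37.78°C
- 100.1°F = 37.83°C
- 100.2°F = 37.89°C
- 100.3°F = 37.94°C

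All four are below 38.0°C and below Grade 1 in Appendix F. The Grade 1 band, 100.4–101.1°F, holds eight readings, so the added range is 4/8 = half its width. This compares widths of the scale, not expected numbers of participants.

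**4. Effect per participant.** One participant whose highest 7-day reading is in the gap moves the fever percentage by:
- 1/100 = 1.0 point in a group of 100;
- 1/50 = 2.0 points in the group of 50;
- about 1/50 = 2.0 or 1/25 = 4.0 points by age, assuming two equal strata.

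These use planned group sizes. Solicited reactions are analysed in the Solicited Safety Set, which may be somewhat smaller.

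**The case against.** The strongest reply is that the figure may never be used. Solicited reactions are graded by protocol Table 6, which is not available here. If fever is derived from that grade, the parenthesis in Section 6.4.1 is only a gloss and no reported number changes. Appendix F applies to clinic vital signs, and Sections 6.3.1 and 6.3.2 define other constructs, so none of them governs solicited fever. The analyses are descriptive, the same rule applies to every group, and the Grade 3 or higher count is untouched.

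Much of this stands as a limit on the consequence. A mismatch between the fever total and its grades needs both the Fahrenheit value to be programmed and Table 6 to start at 100.4°F, and neither can be confirmed. A reading in the gap changes the any-systemic percentage only if the participant reports none of the other six systemic reactions. It changes the any-solicited percentage only if no local reaction is reported either.

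It does not remove the error. The other sections show that the SAP itself uses the correct conversion elsewhere. Table 6 cannot be relied on to cure the problem, because Section 1 of the SAP says that the SAP prevails where its methods differ from the protocol, and Section 7 declares no changes. If Table 6 does start at 100.4°F, that precedence rule gives force to the mistaken figure.

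**Conclusion.** The concern holds. The fever cut-off in Section 6.4.1 is wrong as written: its two units differ by 0.4°F (0.22°C), and the SAP's other pairings contradict it. The conversion is certain. The effect on results is possible but not established: it is nil if the Celsius value or the grade governs. If the Fahrenheit value governs, it is 1.0 point per affected participant in a group of 100 and 2.0 points in the group of 50, on planned sizes. The number of affected participants cannot be derived from the document. No bias between groups is claimed. It should be fixed because it concerns the definition of a component of a primary endpoint.

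**What to change.** In Section 6.4.1, correct the Fahrenheit equivalent of 38.0°C to 100.4°F, and reconcile the sentence with Section 6.3.2, Appendix F and protocol Table 6. Add that diary temperatures are converted to one unit before analysis, and that fever (yes/no) and its severity grade are derived from the same cut-points, so that the fever total equals the sum of the grades.

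The cost is one corrected figure and one derivation rule, with no change to data collection. If programming already uses the Celsius value, no reported number changes. If it uses the Fahrenheit value, the fever count falls by the number of participants whose highest reading is 100.0–100.3°F, and some onset days and durations may shift.

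A separate editorial point can be handled at the same time: the four hemoglobin rows in Appendix E are labelled mg/dL, but values such as 11.0–12.0 are in g/dL. These grades feed the Day 8 shift table in Section 6.4.4, so the label should be corrected. The fever finding does not depend on it.
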